### 13.1.2. Treatment Records

**Table 7: Study Treatment –Implants**

	Biopin 6 1 implant	Biopin 6 2 implants	Placebo 1 to 2 implants
Assessment	(N=xx)	(N=xx)	(N=xx)
Distance to incision from palpable edge of implant 1			
Mean (SD)	xx (xx.x)	xx (xx.x)	xx (xx.x)
Min - Max	xx - xx	xx - xx	xx - xx
Distance to incision from palpable edge of implant 2			
Mean (SD)		xx (xx.x)	xx (xx.x)
Min - Max		xx - xx	xx - xx
Distance to incision from palpable edge of implant 3			
Mean (SD)			xx (xx.x)
Min - Max			xx - xx

**Table 8: Study Treatment –Explants Inspection at Time of Explant**

	Biopin 6 1 implant	Biopin 6 2 implants	Placebo 1 to 2 implants
Assessment	(N=xx)	(N=xx)	(N=xx)
Duration of Implant period (days)			
Mean (SD)	xx (xx.x)	xx (xx.x)	xx (xx.x)
Min - Max	xx - xx	xx - xx	xx - xx
Wound Infection			
N	xx	xx	xx
None, n (%)	xx (xx.x)	xx (xx.x)	xx (xx.x)
Mild, n (%)	xx (xx.x)	xx (xx.x)	xx (xx.x)
Moderate, n (%)	xx (xx.x)	xx (xx.x)	xx (xx.x)
Severe, n (%)	xx (xx.x)	xx (xx.x)	xx (xx.x)
Bleeding			
N	xx	xx	xx
None, n (%)	xx (xx.x)	xx (xx.x)	xx (xx.x)
Mild, n (%)	xx (xx.x)	xx (xx.x)	xx (xx.x)

	Biopin 6 1 implant	Biopin 6 2 implants	Placebo 1 to 2 implants
Assessment	(N=xx)	(N=xx)	(N=xx)
Duration of Implant period (days)			
Mean (SD)	xx (xx.x)	xx (xx.x)	xx (xx.x)
Min - Max	xx - xx	xx - xx	xx - xx
Moderate, n (%)	xx (xx.x)	xx (xx.x)	xx (xx.x)
Severe, n (%)	xx (xx.x)	xx (xx.x)	xx (xx.x)
Scarring			
N	xx	xx	xx
None, n (%)	xx (xx.x)	xx (xx.x)	xx (xx.x)
Mild, n (%)	xx (xx.x)	xx (xx.x)	xx (xx.x)
Moderate, n (%)	xx (xx.x)	xx (xx.x)	xx (xx.x)
Severe, n (%)	xx (xx.x)	xx (xx.x)	xx (xx.x)
Paresthesia			
N	xx	xx	xx
None, n (%)	xx (xx.x)	xx (xx.x)	xx (xx.x)
Perforation			
N	xx	xx	xx
None, n (%)	xx (xx.x)	xx (xx.x)	xx (xx.x)
Implant Migration			
N	xx	xx	xx
None, n (%)	xx (xx.x)	xx (xx.x)	xx (xx.x)
Implant Extrusion			
N	xx	xx	xx
None, n (%)	xx (xx.x)	xx (xx.x)	xx (xx.x)
Wound Dehiscence			
N	xx	xx	xx
None, n (%)	xx (xx.x)	xx (xx.x)	xx (xx.x)
Implant Fragmentation			
N	xx	xx	xx
None, n (%)	xx (xx.x)	xx (xx.x)	xx (xx.x)

### 13.1.3. Pharmacokinetics

**Table 9: Naltrexone Plasma Concentrations Over Time**

Relative Timepoint	Nominal Timepoint (Week)	Biopin 6: 1 implant					Biopin 6: 2 implants				
		N	Mean (ng/mL)	SD (ng/mL)	SEM (ng/mL)	% CV	N	Mean (ng/mL)	SD (ng/mL)	SEM (ng/mL)	% CV
1hr post dose	0.006	x	xx.x	x.xx	x.xx	xx.x	x	xx.x	x.xx	x.xx	xx.x
3hr post dose	0.018	x	xx.x	x.xx	x.xx	xx.x	x	xx.x	x.xx	x.xx	xx.x
6hr post dose	0.036	x	xx.x	x.xx	x.xx	xx.x	x	xx.x	x.xx	x.xx	xx.x
12hr post dose	0.071	x	xx.x	x.xx	x.xx	xx.x	x	xx.x	x.xx	x.xx	xx.x
24hr post dose	0.143	x	xx.x	x.xx	x.xx	xx.x	x	xx.x	x.xx	x.xx	xx.x
48hr post dose	0.286	x	xx.x	x.xx	x.xx	xx.x	x	xx.x	x.xx	x.xx	xx.x
72hr post dose	0.429	x	xx.x	x.xx	x.xx	xx.x	x	xx.x	x.xx	x.xx	xx.x
Day 10	1.000	x	xx.x	x.xx	x.xx	xx.x	x	xx.x	x.xx	x.xx	xx.x
Week 2	1.429	x	xx.x	x.xx	x.xx	xx.x	x	xx.x	x.xx	x.xx	xx.x
Day 7	2.000	x	xx.x	x.xx	x.xx	xx.x	x	xx.x	x.xx	x.xx	xx.x
Week 3	3.000	x	xx.x	x.xx	x.xx	xx.x	x	xx.x	x.xx	x.xx	xx.x
Week 4	4.000	x	xx.x	x.xx	x.xx	xx.x	x	xx.x	x.xx	x.xx	xx.x
Week 5	5.000	x	xx.x	x.xx	x.xx	xx.x	x	xx.x	x.xx	x.xx	xx.x
Week 6	6.000	x	xx.x	x.xx	x.xx	xx.x	x	xx.x	x.xx	x.xx	xx.x
Week 7	7.000	x	xx.x	x.xx	x.xx	xx.x	x	xx.x	x.xx	x.xx	xx.x
Week 8	8.000	x	xx.x	x.xx	x.xx	xx.x	x	xx.x	x.xx	x.xx	xx.x
Week 9	9.000	x	xx.x	x.xx	x.xx	xx.x	x	xx.x	x.xx	x.xx	xx.x
Week 10	10.000	x	xx.x	x.xx	x.xx	xx.x	x	xx.x	x.xx	x.xx	xx.x
Week 11	11.000	x	xx.x	x.xx	x.xx	xx.x	x	xx.x	x.xx	x.xx	xx.x
Pre-explant	12.000	x	xx.x	x.xx	x.xx	xx.x	x	xx.x	x.xx	x.xx	xx.x

		Biopin 6: 1 implant					Biopin 6: 2 implants				
Relative Timepoint	Nominal Timepoint (Week)	N	Mean (ng/mL)	SD (ng/mL)	SEM (ng/mL)	% CV	N	Mean (ng/mL)	SD (ng/mL)	SEM (ng/mL)	% CV
1hr post-explant	12.006	x	xx.x	x.xx	x.xx	xx.x	x	xx.x	x.xx	x.xx	xx.x
3hr post-explant	12.018	x	xx.x	x.xx	x.xx	xx.x	x	xx.x	x.xx	x.xx	xx.x
6hr post-explant	12.036	x	xx.x	x.xx	x.xx	xx.x	x	xx.x	x.xx	x.xx	xx.x
12hr post-explant	12.071	x	xx.x	x.xx	x.xx	xx.x	x	xx.x	x.xx	x.xx	xx.x
24hr post-explant	12.143	x	xx.x	x.xx	x.xx	xx.x	x	xx.x	x.xx	x.xx	xx.x
48hr post-explant	12.286	x	xx.x	x.xx	x.xx	xx.x	x	xx.x	x.xx	x.xx	xx.x
72hr post-explant	12.429	x	xx.x	x.xx	x.xx	xx.x	x	xx.x	x.xx	x.xx	xx.x
96hr post-explant	12.571	x	xx.x	x.xx	x.xx	xx.x	x	xx.x	x.xx	x.xx	xx.x

**Table 10: 6 Beta-Naltrexol Plasma Concentrations Over Time**

Relative Timepoint	Nominal Timepoint (Week)	Biopin 6: 1 implant					Biopin 6: 2 implants				
		N	Mean (ng/mL)	SD (ng/mL)	SEM (ng/mL)	% CV	N	Mean (ng/mL)	SD (ng/mL)	SEM (ng/mL)	% CV
1hr post dose	0.006	x	xx.x	x.xx	x.xx	xx.x	x	xx.x	x.xx	x.xx	xx.x
3hr post dose	0.018	x	xx.x	x.xx	x.xx	xx.x	x	xx.x	x.xx	x.xx	xx.x
6hr post dose	0.036	x	xx.x	x.xx	x.xx	xx.x	x	xx.x	x.xx	x.xx	xx.x
12hr post dose	0.071	x	xx.x	x.xx	x.xx	xx.x	x	xx.x	x.xx	x.xx	xx.x
24hr post dose	0.143	x	xx.x	x.xx	x.xx	xx.x	x	xx.x	x.xx	x.xx	xx.x
48hr post dose	0.286	x	xx.x	x.xx	x.xx	xx.x	x	xx.x	x.xx	x.xx	xx.x
72hr post dose	0.429	x	xx.x	x.xx	x.xx	xx.x	x	xx.x	x.xx	x.xx	xx.x
Day 10	1.000	x	xx.x	x.xx	x.xx	xx.x	x	xx.x	x.xx	x.xx	xx.x
Week 2	1.429	x	xx.x	x.xx	x.xx	xx.x	x	xx.x	x.xx	x.xx	xx.x
Day 7	2.000	x	xx.x	x.xx	x.xx	xx.x	x	xx.x	x.xx	x.xx	xx.x
Week 3	3.000	x	xx.x	x.xx	x.xx	xx.x	x	xx.x	x.xx	x.xx	xx.x
Week 4	4.000	x	xx.x	x.xx	x.xx	xx.x	x	xx.x	x.xx	x.xx	xx.x
Week 5	5.000	x	xx.x	x.xx	x.xx	xx.x	x	xx.x	x.xx	x.xx	xx.x
Week 6	6.000	x	xx.x	x.xx	x.xx	xx.x	x	xx.x	x.xx	x.xx	xx.x
Week 7	7.000	x	xx.x	x.xx	x.xx	xx.x	x	xx.x	x.xx	x.xx	xx.x
Week 8	8.000	x	xx.x	x.xx	x.xx	xx.x	x	xx.x	x.xx	x.xx	xx.x
Week 9	9.000	x	xx.x	x.xx	x.xx	xx.x	x	xx.x	x.xx	x.xx	xx.x
Week 10	10.000	x	xx.x	x.xx	x.xx	xx.x	x	xx.x	x.xx	x.xx	xx.x
Week 11	11.000	x	xx.x	x.xx	x.xx	xx.x	x	xx.x	x.xx	x.xx	xx.x
Pre-explant	12.000	x	xx.x	x.xx	x.xx	xx.x	x	xx.x	x.xx	x.xx	xx.x
1hr post-explant	12.006	x	xx.x	x.xx	x.xx	xx.x	x	xx.x	x.xx	x.xx	xx.x

		Biopin 6: 1 implant					Biopin 6: 2 implants				
Relative Timepoint	Nominal Timepoint (Week)	N	Mean (ng/mL)	SD (ng/mL)	SEM (ng/mL)	% CV	N	Mean (ng/mL)	SD (ng/mL)	SEM (ng/mL)	% CV
3hr post-explant	12.018	x	xx.x	x.xx	x.xx	xx.x	x	xx.x	x.xx	x.xx	xx.x
6hr post-explant	12.036	x	xx.x	x.xx	x.xx	xx.x	x	xx.x	x.xx	x.xx	xx.x
12hr post-explant	12.071	x	xx.x	x.xx	x.xx	xx.x	x	xx.x	x.xx	x.xx	xx.x
24hr post-explant	12.143	x	xx.x	x.xx	x.xx	xx.x	x	xx.x	x.xx	x.xx	xx.x
48hr post-explant	12.286	x	xx.x	x.xx	x.xx	xx.x	x	xx.x	x.xx	x.xx	xx.x
72hr post-explant	12.429	x	xx.x	x.xx	x.xx	xx.x	x	xx.x	x.xx	x.xx	xx.x
96hr post-explant	12.571	x	xx.x	x.xx	x.xx	xx.x	x	xx.x	x.xx	x.xx	xx.x

**Table 11: Pharmacokinetic Parameters**

	Biopin 6 1 implant	Biopin 6 2 implants
Parameter	(N=xx)	(N=xx)
Cmax (ng/mL)		
N	xx	xx
Mean (SD)	xx.x (xx.x)	xx.x (xx.x)
Geometric mean	xx.x	xx.x
Median	xx	xx
Min - Max	xx-xx	xx-xx
tmax (hr)		
N	xx	xx
Mean (SD)	xx.x (xx.x)	xx.x (xx.x)
Geometric mean	xx.x	xx.x
Median	xx	xx
Min - Max	xx-xx	xx-xx
AUC0-4 (h*ng/mL)		
N	xx	xx
Mean (SD)	xx.x (xx.x)	xx.x (xx.x)
Geometric mean	xx.x	xx.x
Median	xx	xx
Min - Max	xx-xx	xx-xx
AUC0-8 (h*ng/mL)		
N	xx	xx
Mean (SD)	xx.x (xx.x)	xx.x (xx.x)
Geometric mean	xx.x	xx.x
Median	xx	xx
Min - Max	xx-xx	xx-xx
AUC0-last (h*ng/mL)		
N	xx	xx
Mean (SD)	xx.x (xx.x)	xx.x (xx.x)
Geometric mean	xx.x	xx.x
Median	xx	xx
Min - Max	xx-xx	xx-xx
AUC∞ (h*ng/mL)		
N	xx	xx
Mean (SD)	xx.x (xx.x)	xx.x (xx.x)
Geometric mean	xx.x	xx.x

	Biopin 6 1 implant	Biopin 6 2 implants
Parameter	(N=xx)	(N=xx)
Median	xx	xx
Min - Max	xx-xx	xx-xx
$\lambda_z$		
N	xx	xx
Mean (SD)	xx.x (xx.x)	xx.x (xx.x)
Geometric mean	xx.x	xx.x
Median	xx	xx
Min - Max	xx-xx	xx-xx
$t_{1/2}$ (hr)		
N	xx	xx
Mean (SD)	xx.x (xx.x)	xx.x (xx.x)
Geometric mean	xx.x	xx.x
Median	xx	xx
Min – Max	xx-xx	xx-xx

#### 13.1.4. Safety

**Table 12: Overall Summary of Adverse Events**

	Biopin 6 1 implant	Biopin 6 2 implants	Placebo 1 to 2 implants
	(N=xx)	(N=xx)	(N=xx)
Number of AEs	xx	xx	xx
Number of SAEs	xx	xx	xx
Number (%) of subjects with at least one AE	xx (xx.x%)	xx (xx.x%)	xx (xx.x%)
Number (%) of subjects with at least one SAE	xx (xx.x%)	xx (xx.x%)	xx (xx.x%)
Number (%) of subjects with at least one AE related  to study product	xx (xx.x%)	xx (xx.x%)	xx (xx.x%)
Number of AEs by severity			
Mild	xx (x.x%)	xx (x.x%)	xx (x.x%)
Moderate	xx (x.x%)	xx (x.x%)	xx (x.x%)
Severe	xx (x.x%)	xx (x.x%)	xx (x.x%)
Life-threatening	xx (x.x%)	xx (x.x%)	xx (x.x%)
Number of AEs by relationship to study product			
At least possibly related	xx (x.x%)	xx (x.x%)	xx (x.x%)
Unrelated	xx (x.x%)	xx (x.x%)	xx (x.x%)

**Table 13: Number and Percentage of Subjects with Adverse Events**

MedDRA System Organ Class/ Preferred Term	Biopin 6 1 implant	Biopin 6 2 implants	Placebo 1 to 2 implants
(N=xx)	(N=xx)		
- Any Adverse Events - SOC	xx (xx.x%)	xx (xx.x%)	xx (xx.x%)
- Overall -	xx (xx.x%)	xx (xx.x%)	xx (xx.x%)
Preferred term 1	xx (xx.x%)	xx (xx.x%)	xx (xx.x%)
Preferred term 2	xx (xx.x%)	xx (xx.x%)	xx (xx.x%)

Notes: Percentages are based on the total number of subjects, as given in the column heading.

Multiple occurrences of a specific adverse event for a subject are counted once in the frequency for the adverse event. Likewise, multiple occurrences of adverse events within a specific preferred term for a subject are counted once in the frequency for the preferred term.

 Fisher's exact test

*Programmer's Notes: Order System Organ Class alphabetically and preferred term alphabetically within System Organ Class.*

**Table 14: Summary of Subjects with Adverse Events by Severity and Relationship – Biopin 6 – 1 Implant**

Number of Subjects (%) (N=x)												
		Mild		Moderate		Severe		Life-threatening		All Grades		
SOC	MedDRA PT	R	NR	R	NR	R	NR	R	NR	R	NR	R + NR
		XX (xx.x%)	XX (xx.x%)	XX (xx.x%)	XX (xx.x%)	XX (xx.x%)	XX (xx.x%)	XX (xx.x%)	XX (xx.x%)	XX (xx.x%)	XX (xx.x%)	XX (xx.x%)

Notes: Events are counted once per subject at the highest severity grade and closest relationship to the investigational product. R= related to investigational product (possibly, probably, definitely). NR = not related to investigational product (unrelated, unlikely).

**Table 15: Summary of Subjects with Adverse Events by Severity and Relationship – Biopin 6 – 2 Implants**

Number of Subjects (%) (N=x)												
		Mild		Moderate		Severe		Life-threatening		All Grades		
SOC	MedDRA PT	R	NR	R	NR	R	NR	R	NR	R	NR	R + NR
		XX (xx.x%)	XX (xx.x%)	XX (xx.x%)	XX (xx.x%)	XX (xx.x%)	XX (xx.x%)	XX (xx.x%)	XX (xx.x%)	XX (xx.x%)	XX (xx.x%)	XX (xx.x%)

Notes: Events are counted once per subject at the highest severity grade and closest relationship to the investigational product. R= related to investigational product (possibly, probably, definitely). NR = not related to investigational product (unrelated, unlikely).

**Table 16: Summary of Subjects with Adverse Events by Severity and Relationship – Placebo**

Number of Subjects (%) (N=x)												
		Mild		Moderate		Severe		Life-threatening		All Grades		
SOC	MedDRA PT	R	NR	R	NR	R	NR	R	NR	R	NR	R + NR
		XX (xx.x%)	XX (xx.x%)	XX (xx.x%)	XX (xx.x%)	XX (xx.x%)	XX (xx.x%)	XX (xx.x%)	XX (xx.x%)	XX (xx.x%)	XX (xx.x%)	XX (xx.x%)

Notes: Events are counted once per subject at the highest severity grade and closest relationship to the investigational product. R= related to investigational product (possibly, probably, definitely). NR = not related to investigational product (unrelated, unlikely).

**Table 17: Number and Percentage of Subjects with Adverse Events Occurring in  $\geq 5\%$  of Subjects**

MedDRA SOC/	Biopin 6 1 implant	Biopin 6 2 implants	Placebo 1 to 2 implants
Preferred Term	(N=xx)	(N=xx)	(N=xx)
SOC			
- Overall -	xx (xx.x%)	xx (xx.x%)	xx (xx.x%)
Preferred term 1	xx (xx.x%)	xx (xx.x%)	xx (xx.x%)
Preferred term 2	xx (xx.x%)	xx (xx.x%)	xx (xx.x%)

Notes: Percentages are based on the total number of subjects, as given in the column heading.

Multiple occurrences of a specific adverse event for a subject are counted once in the frequency for the adverse event. Likewise, multiple occurrences of adverse events within a specific preferred term for a subject are counted once in the frequency for the preferred term. At least 5% occurring in either arm to be included in the table.

 Fisher's Exact test

*Programmer's Notes: Order System Organ Class alphabetically and preferred term alphabetically within System Organ Class.*

**Table 18: Number and Percentage of Subjects with Adverse Events by Maximum Severity**

MedDRA SOC/ Preferred Term	Biopin 6 -1 implant				Biopin 6 -2 implants			
	(N=xx)				(N=xx)			
	Mild	Moderate	Severe	Life- threatening	Mild	Moderate	Severe	Life- threatening
- Any Adverse Events - SOC	xx (xx.x%)	xx (xx.x%)	xx (xx.x%)	xx (xx.x%)	xx (xx.x%)	xx (xx.x%)	xx (xx.x%)	xx (xx.x%)
- Overall -	xx (xx.x%)	xx (xx.x%)	xx (xx.x%)	xx (xx.x%)	xx (xx.x%)	xx (xx.x%)	xx (xx.x%)	xx (xx.x%)
Preferred term 1	xx (xx.x%)	xx (xx.x%)	xx (xx.x%)	xx (xx.x%)	xx (xx.x%)	xx (xx.x%)	xx (xx.x%)	xx (xx.x%)
Preferred term 2	xx (xx.x%)	xx (xx.x%)	xx (xx.x%)	xx (xx.x%)	xx (xx.x%)	xx (xx.x%)	xx (xx.x%)	xx (xx.x%)

MedDRA SOC/ Preferred Term	Placebo 1 to 2 implants			
	(N=xx)			
	Mild	Moderate	Severe	Life- threatening
- Any Adverse Events - SOC	xx (xx.x%)	xx (xx.x%)	xx (xx.x%)	xx (xx.x%)
- Overall -	xx (xx.x%)	xx (xx.x%)	xx (xx.x%)	xx (xx.x%)
Preferred term 1	xx (xx.x%)	xx (xx.x%)	xx (xx.x%)	xx (xx.x%)
Preferred term 2	xx (xx.x%)	xx (xx.x%)	xx (xx.x%)	xx (xx.x%)

Notes: Percentages are based on the total number of subjects, as given in the column heading.

Multiple occurrences of a specific adverse event for a subject are counted once in the frequency for the adverse event. Likewise, multiple occurrences of adverse events within a specific preferred term for a subject are counted once in the frequency for the preferred term.

*Programmer's Notes: Order System Organ Class alphabetically and preferred term alphabetically within System Organ Class.*

**Table 19: Number and Percentage of Subjects with Adverse Events Leading to Discontinuation of Study**

MedDRA SOC/	Biopin 6 1 implant	Biopin 6 2 implants	Placebo 1 to 2 implants
Preferred Term	(N=xx)	(N=xx)	(N=xx)
SOC			
- Overall -	xx (xx.x%)	xx (xx.x%)	xx (xx.x%)
Preferred term 1	xx (xx.x%)	xx (xx.x%)	xx (xx.x%)
Preferred term 2	xx (xx.x%)	xx (xx.x%)	xx (xx.x%)

Notes: Percentages are based on the total number of subjects, as given in the column heading.

Multiple occurrences of a specific adverse event for a subject are counted once in the frequency for the adverse event. Likewise, multiple occurrences of adverse events within a specific preferred term for a subject are counted once in the frequency for the preferred term.

*Programmer's Notes: Order System Organ Class alphabetically and preferred term alphabetically within System Organ Class.*

**Table 20: Number and Percentage of Subjects with Adverse Events Leading to Early Explant**

MedDRA SOC/	Biopin 6 1 implant	Biopin 6 2 implants	Placebo 1 to 2 implants
Preferred Term	(N=xx)	(N=xx)	(N=xx)
SOC			
- Overall -	xx (xx.x%)	xx (xx.x%)	xx (xx.x%)
Preferred term 1	xx (xx.x%)	xx (xx.x%)	xx (xx.x%)
Preferred term 2	xx (xx.x%)	xx (xx.x%)	xx (xx.x%)

Notes: Percentages are based on the total number of subjects, as given in the column heading.

Multiple occurrences of a specific adverse event for a subject are counted once in the frequency for the adverse event. Likewise, multiple occurrences of adverse events within a specific preferred term for a subject are counted once in the frequency for the preferred term.

*Programmer's Notes: Order System Organ Class alphabetically and preferred term alphabetically within System Organ Class.*

**Table 21: Incision Site Visual Inspection**

	Biopin 6 1 implant	Biopin 6 2 implants	Placebo 1 to 3 implants
Assessment	(N=xx)	(N=xx)	(N=xx)
Repeat for each visit: Day 1, 2, 3, 4, 7, 10, Weeks 2, 3, 4, 5, 6, 7, 8, 9, 10, 11, 12			
Wound Infection			
N	xx	xx	xx
None, n (%)	xx (xx.x)	xx (xx.x)	xx (xx.x)
Mild, n (%)	xx (xx.x)	xx (xx.x)	xx (xx.x)
Moderate, n (%)	xx (xx.x)	xx (xx.x)	xx (xx.x)
Severe, n (%)	xx (xx.x)	xx (xx.x)	xx (xx.x)
Bleeding			
N	xx	xx	xx
None, n (%)	xx (xx.x)	xx (xx.x)	xx (xx.x)
Mild, n (%)	xx (xx.x)	xx (xx.x)	xx (xx.x)
Moderate, n (%)	xx (xx.x)	xx (xx.x)	xx (xx.x)
Severe, n (%)	xx (xx.x)	xx (xx.x)	xx (xx.x)
Scarring			
N	xx	xx	xx
None, n (%)	xx (xx.x)	xx (xx.x)	xx (xx.x)
Mild, n (%)	xx (xx.x)	xx (xx.x)	xx (xx.x)
Moderate, n (%)	xx (xx.x)	xx (xx.x)	xx (xx.x)
Severe, n (%)	xx (xx.x)	xx (xx.x)	xx (xx.x)
Paresthesia			
N	xx	xx	xx
None, n (%)	xx (xx.x)	xx (xx.x)	xx (xx.x)
Perforation			
N	xx	xx	xx
None, n (%)	xx (xx.x)	xx (xx.x)	xx (xx.x)
Implant Migration			
N	xx	xx	xx
None, n (%)	xx (xx.x)	xx (xx.x)	xx (xx.x)
Implant Extrusion			
N	xx	xx	xx
None, n (%)	xx (xx.x)	xx (xx.x)	xx (xx.x)
Wound Dehiscence			
N	xx	xx	xx
None, n (%)	xx (xx.x)	xx (xx.x)	xx (xx.x)

**Table 22: Suicidal Ideation or Suicide Attempt (CSSR-S)**

	Biopin 6 1 implant	Biopin 6 2 implants	Placebo 1 to 2 implants
Assessment	(N=xx)	(N=xx)	(N=xx)
Repeat for each visit: Screening, Day -1, Weeks 4, 8, and 12			
Suicidal Ideation			
n (%)	xx (xx.x)	xx (xx.x)	xx (xx.x)
Suicide Attempt			
n (%)	xx (xx.x)	xx (xx.x)	xx (xx.x)

**Table 23: HAM-D17 Scores**

	Biopin 6 1 implant	Biopin 6 2 implants	Placebo 1 to 2 implants
Assessment	(N=xx)	(N=xx)	(N=xx)
Repeat for each visit: Screening, Day -1, Weeks 2, 4, 6, 8, and 12			
N	xx	xx	xx
Mean (SD)	xx.x (xx.x)	xx.x (xx.x)	xx.x (xx.x)
Median	xx	xx	xx
Min - Max	xx-xx	xx-xx	xx-xx

**Table 24: HAM-D17 Number and Percentage of Patients with Scores Indicative of Clinical Depression (Scored > 7)**

	Biopin 6 1 implant	Biopin 6 2 implants	Placebo 1 to 2 implants
Assessment	(N=xx)	(N=xx)	(N=xx)
Repeat for each visit: Screening, Day -1, Weeks 4, 8, and 12			
n (%)	xx (xx.x)	xx (xx.x)	xx (xx.x)

**Table 25: Summary of Blood Chemistries**

	Biopin 6 1 implant	Biopin 6 2 implants	Placebo 1 to 2 implants
	(N=xx)	(N=xx)	(N=xx)
Repeat for each visit: Screening, Day -1, Day 3, Weeks 4 and 8			
Test Name (units)			
N	xx	xx	xx
Mean (SD)	xx.x (xx.x)	xx.x (xx.x)	xx.x (xx.x)
Min - Max	xx-xx	xx-xx	xx-xx
Change from baseline at Day -1, Day 3, Weeks 4 and 8			
N	xx	xx	xx
Mean (SD)	xx.x (xx.x)	xx.x (xx.x)	xx.x (xx.x)
Min - Max	xx-xx	xx-xx	xx-xx

Programmers note: table will include alanine aminotransferase, albumin, alkaline phosphatase, aspartate aminotransferase, bilirubin (total and direct), calcium, chloride, cholesterol, creatinine, GGT, glucose, phosphate, potassium, sodium, total protein, uric acid, and BUN.

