## **8.4 Week 12 and 14: study end**

Subjects will return for a residential visit on week 12 after dosing. Prior to removal, the implant **parameters required by Appendix A** will be assessed (distance from incision, photo of site) as

per after-implantation. At that time, the implant will be removed (Appendix B) and be subject to Gross and microscopic descriptions and photos of each tissue capsule. Blood will be taken for PK pre-explant and 1, 3, 6, 12, 24, 48, 72, 96 hrs after explant. Sampling up to 24 hrs will be as residents; sampling at 48, 72, and 96 hrs (+/- 4 hrs) will be as non-residents. Repeat assessment will be made of adverse effects, vital signs, clinical chemistry, hematology, EKG, concomitant medications, urine drugs, suicidality, depression.

On week 14, 2 weeks after implant removal, the subjects will return for a non-residential visit for surgical evaluation of the implant removal site.

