## Protocol Timetable

Study Phase	Screening (days -28 to -2)	Day -1	Day 1 to Week 11 	Week 12 (and week 14) 
Informed consent	X			
Demographic data 	X			
Medical history	X	X (update if needed)		
Physical exam 	X	X (update if needed)	Week 4 and 8	X
Weight/height	X			
Urine drugs of abuse screen 	X	X	Week 4 and 8	X
Alcohol breath test	X			
Naloxone challenge test	X	X		
Concomitant medications	X	X	Weekly	X
Serology 	X	X		
Birth Control Methods/Pregnancy Test 	X	X		
C-SSRS for suicidality	X	X	Weeks 4 and 8	X
HAM-D for depression	X	X	Weeks 2,4,6,8,10	X
Inclusion/exclusion criteria	X	X		
Randomization 		X		
Residential visits		Check in on day (-1)	Check out on Day 4 (72 hours postdose)	Week 12
Non-residential visits	X		Days 7 and 10, and Weeks 2, 3, 4, 5, 6, 7, 8, 9, 10, 11	Week 12 (week 14)
Study drug (Biopin or placebo) administration by implantation			Day 1 (0 h): Insert BIOPIN implant	Remove BIOPIN implant (and week 14) 
Implant Tissue Assessment			At each residential and non-residential visit	Gross and microscopic descriptions and photos of each tissue capsule.

 Age, gender, and race/ethnicity

 Abbreviated exam

 Amphetamines, barbiturates, benzodiazepines, cocaine, opiates, cannabinoids, phencyclidine, propoxyphene, methadone.

 Hepatitis B surface antigen, hepatitis C antibody, human immunodeficiency (HIV-1 and HIV-2) antibodies and p24 antigen, covid antigen

 Serum HCG test at screening; urine HCG test at day (-1. For postmenopausal females, a follicle stimulating hormone test will be performed during screening.

 Each dose cohort of 8 subjects randomized 6 active vs 2 placebo

Study Phase	Screening (days -28 to -2)	Day -1	Day 1 to Week 11 	Week 12 (and week 14) 
Safety and tolerability:				
Adverse event recording	X		Predose, 8, 24, 48 and 72 hours postdose. Then weekly	X
Vital signs 	X		Predose, 8, 24, 48 and 72 hours postdose. Weeks 4 and 8.	X (pre and post explant)
12-lead ECG	X	X	Week 4 and 8	X (pre and post explant)
Clinical chemistries 	X		72 hours post dose; then weeks 4 and 8	X
Hematology 	X		72 hours post dose; then weeks 4 and 8	X
Coagulation 	X			
Pharmacokinetics (naltrexone and its major metabolite, 6-beta-naltrexol)				

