### **9.7.4 Clinical Laboratory**

Descriptive statistics will be generated for all tests performed at screening and at each clinic visit. If a laboratory analysis is repeated, the last measurement performed prior to the clinic visit will be used in the summary statistics for that clinic visit. If an unscheduled clinical laboratory visit occurs prior to a scheduled visit that is missed due to dropout, then the unscheduled visit will be used in the summary statistics for the missed scheduled clinical visit. If an unscheduled clinical laboratory visit occurs between two scheduled clinical visits, then the data from the unscheduled visit will only be presented in the listings and not in summary statistics. In addition, at each post-randomization clinic visit descriptive statistics for change from baseline will be generated for clinical chemistry and hematology tests. Laboratory values will be plotted as mean  $\pm$  standard error over time. All laboratory measurements will be presented in the listings including an assessment if the laboratory value is considered within normal limits or is not clinically significant or is clinically significant.

The number and percentage of positive urine drug tests and pregnancy tests for screening visits and all treatment and follow-up visits will be tabulated. Results of all urine drug tests and pregnancy tests will be presented in the listings. The percentage of subjects with a positive urine drug test at any time post start of treatment will also be presented by test type and treatment group.

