**Table 26: Summary of Hematology Tests**

	Biopin 6 1 implant	Biopin 6 2 implants	Placebo 1 to 2 implants
	(N=xx)	(N=xx)	(N=xx)
Repeat for each visit: Screening, Day -1, Day 3, Weeks 4 and 8			
Test Name (units)			
N	xx	xx	xx
Mean (SD)	xx.x (xx.x)	xx.x (xx.x)	xx.x (xx.x)
Min - Max	xx-xx	xx-xx	xx-xx
Change from baseline at Day -1, Day 3, Weeks 4 and 8			
N	xx	xx	xx
Mean (SD)	xx.x (xx.x)	xx.x (xx.x)	xx.x (xx.x)
Min - Max	xx-xx	xx-xx	xx-xx

Programmers note: Hemoglobin, hematocrit, red blood cell count (RBC), reticulocytes, white blood cell count (WBC), and platelets.

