**Table 28: Summary of Positive Urine Drug Tests**

	Number positive (%)		
	Biopin 6 1 implant	Biopin 6 2 implants	Placebo 1 to 2 implants
Test	(N=xx)	(N=xx)	(N=xx)
Timepoints include: Screening, Day -1, Weeks 4, 8, and 12			
Amphetamine	xx (xx.x%)	xx (xx.x%)	xx (xx.x%)
Barbiturates	xx (xx.x%)	xx (xx.x%)	xx (xx.x%)
Benzodiazapines	xx (xx.x%)	xx (xx.x%)	xx (xx.x%)
Cocaine	xx (xx.x%)	xx (xx.x%)	xx (xx.x%)
Opiates	xx (xx.x%)	xx (xx.x%)	xx (xx.x%)
cannabinoids	xx (xx.x%)	xx (xx.x%)	xx (xx.x%)
phencyclidine	xx (xx.x%)	xx (xx.x%)	xx (xx.x%)
propoxyphene	xx (xx.x%)	xx (xx.x%)	xx (xx.x%)
methadone	xx (xx.x%)	xx (xx.x%)	xx (xx.x%)

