**Table 30: Summary of ECG Results**

	Biopin 6 1 implant	Biopin 6 2 implants	Placebo 1 to 2 implants
Result	(N=xx)	(N=xx)	(N=xx)
Screening			
Normal	xx (xx.x%)	xx (xx.x%)	xx (xx.x%)
Abnormal, Not Clinically Significant	xx (xx.x%)	xx (xx.x%)	xx (xx.x%)
Abnormal, Clinically Significant	xx (xx.x%)	xx (xx.x%)	xx (xx.x%)
Other time points include Day -1, Weeks 4 and 8			
Normal	xx (xx.x%)	xx (xx.x%)	xx (xx.x%)
Abnormal, Not Clinically Significant	xx (xx.x%)	xx (xx.x%)	xx (xx.x%)
Abnormal, Clinically Significant	xx (xx.x%)	xx (xx.x%)	xx (xx.x%)

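### The shells for SAP Tables 25, 26, 29 and 30 stop at Week 8, so the scheduled Week 12 laboratory tests, vital signs and ECGs have no row in the by-visit safety tables

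*SAP*

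**What the plan says.** **Shells.** Tables 25 and 26 carry the same visit line, "Repeat for each visit: Screening, Day -1, Day 3, Weeks 4 and 8", and the same change line, "Change from baseline at Day -1, Day 3, Weeks 4 and 8". Table 30 gives Screening and then "Other time points include Day -1, Weeks 4 and 8". Table 29 lists Screening, Day -1, Day 1 predose, 8, 24, 48 and 72 hours, and Weeks 4 and 8; its change-from-baseline row also ends at Week 8.

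**Schedule.** In the SAP timetable, chemistry and hematology are due at "72 hours post dose; then weeks 4 and 8", with a further mark in the Week 12 column. For vital signs and ECG that column reads "X (pre and post explant". Protocol 8.4 says of the Week 12 visit: "Repeat assessment will be made of adverse effects, vital signs, clinical chemistry, hematology, EKG, concomitant medications, urine drugs, suicidality, depression". Week 14 is a surgical check of the explant site only.

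**Analysis text.** SAP 9.7.4 states: "Descriptive statistics will be generated for all tests performed at screening and at each clinic visit". It adds laboratory change from baseline at every clinic visit after randomization. SAP 9.6.3 promises ECG percentages for every time point. SAP 5.2 puts the safety analysis over the whole of treatment and follow-up. Protocol 9.2 commits to a summary table of laboratory values at every time point.

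**The concern.** Week 12 is the only scheduled laboratory, vital-sign and ECG assessment made after the full implant period. Protocol 5.2 says that subjects are followed for hepatotoxicity and reticulocytes, and laboratory safety is a secondary objective of this first-in-human study. A programmer who follows the shells would produce by-visit tables whose last row is Week 8. A shift in liver enzymes, reticulocytes or blood pressure that arose between Weeks 8 and 12 would then not show in any tabulated change from baseline.

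Subjects who leave after Week 8 are affected too. Protocol 7.6.2 seeks a final chemistry and hematology panel at early explantation. SAP 9.7.4 lets an unscheduled panel stand in for a scheduled visit missed through dropout. Without a Week 12 row, that rule has nowhere to place such a panel.

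**Working it through.** No power, alpha or sample-size figure bears on this, and the plan states no figure of its own to reproduce. The check sets the schedule beside the shells and counts post-dose assessments. I read Day 3 in Tables 25 and 26 as the 72-hour panel.

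| Assessment (shell) | Scheduled after dosing | In the shell | No row |
|---|---|---|---|
| Chemistry (Table 25) | 72 h, Weeks 4, 8, 12 = 4 | Day 3, Weeks 4, 8 = 3 | 4 − 3 = 1 of 4 |
| Hematology (Table 26) | 72 h, Weeks 4, 8, 12 = 4 | Day 3, Weeks 4, 8 = 3 | 4 − 3 = 1 of 4 |
| ECG (Table 30) | Weeks 4, 8, Week 12 pre, Week 12 post = 4 | Weeks 4, 8 = 2 | 4 − 2 = 2 of 4 |
| Vital signs (Table 29), SAP timetable | 8, 24, 48, 72 h, Weeks 4, 8, Week 12 pre, Week 12 post = 8 | 8, 24, 48, 72 h, Weeks 4, 8 = 6 | 8 − 6 = 2 of 8 |
| Vital signs (Table 29), Protocol timetable | 4 (8 to 72 h) + 2 (Days 7, 10) + 10 (Weeks 2 to 11) + 2 (Week 12 pre, post) = 18 | 6 | 18 − 6 = 12 of 18 |

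The last tabulated visit is Week 8 of a 12-week implant period. The stretch with no by-visit row is (12 − 8)/12 = 1/3 of that period.

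Vital signs have two rows because the documents disagree. The Protocol timetable and Protocol 8.3 list Days 7 and 10 and Weeks 2 to 11. The SAP timetable and the follow-up paragraph of the Protocol synopsis still list Weeks 4 and 8. The SAP names Protocol version 5.0 as its source. On either schedule, Week 12 is missing from Table 29.

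Is the omission a choice or a slip?

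- Tables 21, 22, 23, 24 and 28 all carry Week 12. Table 28, for example, reads "Timepoints include: Screening, Day -1, Weeks 4, 8, and 12".
- No reason is given for ending the other four shells at Week 8.
- Tables 25 and 26 list Day -1, where neither timetable schedules chemistry or hematology and Protocol 8.2 names neither.
- Table 27 is titled as screening only, yet carries the same multi-visit line.

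This pattern fits a copied template line better than a decision about Week 12.

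**The case against.** The strongest reply is that the text governs and already includes Week 12. SAP 2 calls the tables samples, the wording of Table 30 need not be exhaustive, and SAP 12 has tables reviewed for consistency with the plan. The text does show that dropping Week 12 was not intended. It does not settle what gets programmed: the same SAP says that the sample tables will be populated, and a check against a plan that disagrees with itself can pass either version. Table 28 uses the same verb as Table 30 and then gives its full scheduled list, Week 12 included.

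The second reply is that little is at stake. The study is descriptive with no hypotheses, PK is primary, and two cohorts of 8 make 16 planned subjects, whose listings can be read in full. Each table would also print its visits, so the gap would be visible. All of this stands, and it keeps the point below a must-fix.

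A reader might infer that a Week 12 laboratory change would be seen only in listings. The documents do not support that. Figures 1 and 2 plot chemistry and hematology over time with no visit cut-off, Protocol 10.6 has clinically significant laboratory values reported as AEs, and Protocol 9.2 has individual abnormal values presented and discussed. Figure 3 likewise sets no visit limit for vital signs. What remains is narrower: figures show group means rather than tabulated change, and no figure covers ECG.

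A reader might also suspect that Week 12 was left out after the results were seen, because SAP 3 says that the plan was finalized once dose-level 2 data were available. Nothing in the documents supports this, and the signs of template carry-over point the other way.

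**Conclusion.** The point holds as an internal inconsistency in the SAP, of should-fix weight. The shells for Tables 25, 26, 29 and 30 conflict with the timetables, Protocol 8.4 and SAP 5.2. The laboratory shells also conflict with Protocol 9.2 and SAP 9.7.4, and the ECG shell with SAP 9.6.3. Populated as drawn, they leave out 1 of 4 post-dose panels for chemistry and for hematology, 2 of 4 post-dose ECGs, and both Week 12 vital-sign sets. No table would give Week 12 change from baseline.

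No data are lost and no estimate is biased. The size of any clinical signal at risk cannot be stated from these documents. The dog exposure values in Protocol 7.8.2 might tempt a reader to weight the last four weeks, but they say nothing about human laboratory findings or about which visits are tabulated.

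The conclusion assumes that the shells are programmed as printed and that Day 3 means the 72-hour panel.

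**What to change.** - **Tables 25 and 26:** add Week 12 rows for value and change from baseline. Remove the Day -1 rows. Screening is then the only scheduled pre-dose panel, so name it as baseline in a footnote.
- **Table 29:** add Week 12 pre-explant and post-explant rows, for value and change. Add the Day 7, Day 10 and weekly visits of the current protocol, and reconcile the SAP timetable and the Protocol synopsis with the Protocol timetable and Protocol 8.3.
- **Table 30:** add Week 12 pre-explant and post-explant rows.

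Figures 1 to 3 need no change on this point, only confirmation that Week 12 is plotted. Tabulated post-dose assessments then rise from 3 of 4 to 4 of 4 for chemistry and hematology, and from 2 of 4 to 4 of 4 for ECG. The cost is an edit to four shells and one timetable row in the SAP, plus the synopsis line in the protocol. The assessments are already scheduled, so no new data collection is needed.
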